5.3.5.7 Abnormal Liver Function Tests

The finding of an elevated ALT or AST ($>3 \times$ baseline value) in combination with either an elevated total bilirubin ($>2 \times$ ULN) or clinical jaundice in the absence of cholestasis or other causes of hyperbilirubinemia is considered to be an indicator of severe liver injury (as defined by Hy's law). Therefore, investigators must report as an adverse event the occurrence of either of the following:

- Treatment-emergent ALT or AST $>3 \times$ baseline value in combination with total bilirubin $>2 \times$ ULN (of which $\geq 35\%$ is direct bilirubin)
- Treatment-emergent ALT or AST $>3 \times$ baseline value in combination with clinical jaundice

The most appropriate diagnosis or (if a diagnosis cannot be established) the abnormal laboratory values should be recorded on the Adverse Event eCRF (see Section 5.3.5.2) and reported to the Sponsor immediately (i.e., no more than 24 hours after learning of the event), either as a serious adverse event or an adverse event of special interest (see Section 5.4.2).

5.3.5.8 Deaths

All deaths that occur during the protocol-specified adverse event reporting period (see Section 5.3.1), regardless of relationship to study drug, must be recorded on the Adverse Event eCRF and immediately reported to the Sponsor (see Section 5.4.2). This includes death attributed to progression of NSCLC.

Death should be considered an outcome and not a distinct event. The event or condition that caused or contributed to the fatal outcome should be recorded as the single medical concept on the Adverse Event eCRF. Generally, only one such event should be reported. If the cause of death is unknown and cannot be ascertained at the time of reporting, "unexplained death" should be recorded on the Adverse Event eCRF. If the cause of death later becomes available (e.g., after autopsy), "unexplained death" should be replaced by the established cause of death. The term "sudden death" should not be used unless combined with the presumed cause of death (e.g., "sudden cardiac death"). If the cause of death later becomes available (e.g., after autopsy), "unexplained death" should be replaced by the established cause of death.

If the death is attributed to progression of NSCLC, this is the only case when "disease progression" should be recorded on the Adverse Event eCRF.

Deaths that occur after the adverse event reporting period should be reported as described in Section 5.6.

5.3.5.9 Preexisting Medical Conditions

A preexisting medical condition is one that is present at the screening visit for this study. Such conditions should be recorded on the General Medical History and Baseline Conditions eCRF.

A preexisting medical condition should be recorded as an adverse event only if the frequency, severity, or character of the condition worsens during the study. When recording such events on the Adverse Event eCRF, it is important to convey the concept that the preexisting condition has changed by including applicable descriptors (e.g., "more frequent headaches").

5.3.5.10 Lack of Efficacy or Worsening of Non-Small Cell Lung Cancer

Deterioration that is judged by the investigator to have unexpectedly worsened in severity or frequency or changed in nature (i.e., deterioration beyond the expected pattern of progression of the underlying disease) should be recorded as an adverse

event. When recording an unanticipated worsening of non-small cell lung cancer on the Adverse Event eCRF, it is important to convey the concept that the condition has changed by including applicable descriptors (e.g., "accelerated worsening of non-small cell lung cancer").

Events that are clearly consistent with the expected pattern of progression of the underlying disease should not be recorded as adverse events, unless death is the outcome (see Section 5.3.5.8). These data will be captured as efficacy assessment data only. In most cases, the expected pattern of progression will be based on RECIST v1.1. In rare cases, the determination of clinical progression will be based on symptomatic deterioration. However, every effort should be made to document progression through use of objective criteria. If there is any uncertainty as to whether an event is due to disease progression/recurrence, it should be reported as an adverse event.

5.3.5.11 Hospitalization or Prolonged Hospitalization

Any adverse event that results in hospitalization (i.e., inpatient admission to a hospital) or prolonged hospitalization should be documented and reported as a serious adverse event (per the definition of serious adverse event in Section 5.2.2), except as outlined below.

An event that leads to hospitalization under the following circumstances should not be reported as an adverse event or a serious adverse event:

- Hospitalization for respite care
- Planned hospitalization required by the protocol (e.g., for study drug administration)
- Hospitalization for a preexisting condition, provided that all of the following criteria are met:

The hospitalization was planned prior to the study or was scheduled during the study when elective surgery became necessary because of the expected normal progression of the disease

The patient has not experienced an adverse event

- Hospitalization due solely to progression of the underlying cancer

An event that leads to hospitalization under the following circumstances is not considered to be a serious adverse event, but should be reported as an adverse event instead:

- Hospitalization that was necessary because of patient requirement for outpatient care outside of normal outpatient clinic operating hours

5.3.5.12 Adverse Events Associated with an Accidental Overdose or Medication Error in Drug Administration

An overdose is the accidental or intentional use of a drug in an amount higher than the dose being studied. Medication error: Accidental deviation in the administration of a

drug, in some cases, a medication error may be intercepted prior to administration of the drug.

An overdose or incorrect administration of atezolizumab treatment is not itself an adverse event, but it may result in an adverse event. All adverse events associated with an overdose, incorrect administration or medication error of study drug should be recorded on the Adverse Event eCRF. If the associated adverse event fulfills seriousness criteria or qualifies as an adverse event of special interest, the event should be reported to the Sponsor immediately (i.e., no more than 24 hours after learning of the event; see Section [5.4.2](#)).

5.4 IMMEDIATE REPORTING REQUIREMENTS FROM INVESTIGATOR TO SPONSOR

Certain events require immediate reporting to allow the Sponsor to take appropriate measures to address potential new risks in a clinical trial. The investigator must report such events to the Sponsor immediately; under no circumstances should reporting take place more than 24 hours after the investigator learns of the event. The following is a list of events that the investigator must report to the Sponsor within 24 hours after learning of the event, regardless of relationship to study drug:

- Serious adverse events (see Section [5.4.2](#) for further details)
- Adverse events of special interest (see Section [5.4.2](#) for further details)
- Pregnancies (see Section [5.4.3](#) for further details)

For serious adverse events and adverse events of special interest, the investigator must report new significant follow-up information for these events to the Sponsor immediately (i.e., no more than 24 hours after becoming aware of the information). New significant information includes the following:

- New signs or symptoms or a change in the diagnosis
- Significant new diagnostic test results
- Change in causality based on new information
- Change in the event's outcome, including recovery
- Additional narrative information on the clinical course of the event

Investigators must also comply with local requirements for reporting serious adverse events to the local health authority and Institutional Review Board (IRB)/Ethics Committee (EC).

5.4.2 Reporting Requirements for Serious Adverse Events and Adverse Events of Special Interest

5.4.2.1 Events That Occur prior to Study Drug Initiation

After informed consent has been obtained but prior to initiation of study drug, only serious adverse events caused by a protocol-mandated intervention should be reported. *The paper Clinical Trial Adverse Event/Special Situations Form* provided to investigators should be completed and submitted to the Sponsor or its designee immediately (i.e., no more than 24 hours after learning of the event), either by faxing or by scanning and emailing the form using the fax number or email address provided to investigators.

5.4.2.2 Events That Occur after Study Drug Initiation

After initiation of study drug, adverse events will be reported until 30 days after the last dose of atezolizumab (neoadjuvant or adjuvant, whichever occurs last). See [Table 5](#) for full details. Serious adverse events and adverse events of special interest will be reported until 90 days after the last dose of atezolizumab (neoadjuvant or adjuvant, whichever occurs last). Only serious adverse events associated with CT scans, blood sample collection, and optional biopsy at the time of disease progression/recurrence that occur after the 90 day reporting window, but during the Surveillance period, will be collected and reported (see [Table 5](#)). Investigators should record all case details that can be gathered immediately (i.e., within 24 hours after learning of the event) on the Adverse Event eCRF and submit the report via the electronic data capture (EDC) system. A report will be generated and sent to Safety Risk Management by the EDC system.

In the event that the EDC system is unavailable, the *paper Clinical Trial Adverse Event/Special Situations Form* provided to investigators should be completed and submitted to the Sponsor or its designee immediately (i.e., no more than 24 hours after learning of the event), either by faxing or by scanning and emailing the form using the fax number or email address provided to investigators. Once the EDC system is available, all information will need to be entered and submitted via the EDC system.

Instructions for reporting serious adverse events that occur >90 days after the last dose of atezolizumab are provided in Section [5.6](#).

5.4.3 Reporting Requirements for Pregnancies

5.4.3.1 Pregnancies in Female Patients

Female patients of childbearing potential will be instructed through the Informed Consent Form to immediately inform the investigator if they become pregnant during the study or within 5 months after the final dose of atezolizumab. A *paper* Clinical Trial Pregnancy Reporting Form should be completed and submitted to the Sponsor or its designee immediately (i.e., no more than 24 hours after learning of the pregnancy), either by faxing or by scanning and emailing the form using the fax number or email address provided to investigators. Pregnancy should not be recorded on the Adverse Event eCRF. The investigator should discontinue study drug and counsel the patient, discussing the risks of the pregnancy and the possible effects on the fetus. Monitoring of the patient should continue until conclusion of the pregnancy. Any serious adverse events associated with the pregnancy (e.g., an event in the fetus, an event in the mother during or after the pregnancy, or a congenital anomaly/birth defect in the child) should be reported on the Adverse Event eCRF. In addition, the investigator will submit a Clinical Trial Pregnancy Reporting Form when updated information on the course and outcome of the pregnancy becomes available.

Attempts should be made to collect and report infant health information. When permitted by the site, an Authorization for the Use and Disclosure of Infant Health Information would need to be signed by one or both parents (as per local regulations) to allow for follow-up on the infant. If the authorization has been signed, the infant's health status at birth should be recorded on the Clinical Trial Pregnancy Reporting Form. In addition, the Sponsor may collect follow-up information on the infant's health status at 6 and 12 months after birth.

5.4.3.2 Abortions

A spontaneous abortion should be classified as a serious adverse event (as the Sponsor considers abortions to be medically significant), recorded on the Adverse Event eCRF, and reported to the Sponsor immediately (i.e., no more than 24 hours after learning of the event; see Section [5.4.2](#)).

If a therapeutic or elective abortion was performed because of an underlying maternal or embryofetal toxicity, the toxicity should be classified as a serious adverse event, recorded on the Adverse Event eCRF, and reported to the Sponsor immediately (i.e., no more than 24 hours after learning of the event; see Section [5.4.2](#)). A therapeutic or elective abortion performed for reasons other than an underlying maternal or embryofetal toxicity is not considered an adverse event.

All abortions should be reported as pregnancy outcomes on the *paper* Clinical Trial Pregnancy Reporting Form.

5.4.3.3 Congenital Anomalies/Birth Defects and Abortions

Any congenital anomaly/birth defect in a child born to a female patient exposed to study drug should be classified as a serious adverse event, recorded on the Adverse Event eCRF, and reported to the Sponsor immediately (i.e., no more than 24 hours after learning of the event; see Section 5.4.2). Any abortion should be reported in the same fashion (as the Sponsor considers abortions to be medically significant).

5.4.4 Reporting Requirements for Special Situations and Non-Serious Adverse Events Associated with a Special Situation

After initiation of study drug, special situations and adverse events associated with special situations will be reported until 90 days after the final dose of study drug. Investigators should record all case details that can be gathered on the Adverse Event eCRF and submit the report via the electronic data capture (EDC) system within 30 calendar days of awareness. A report will be generated and sent to Roche Safety Risk Management by the EDC system.

5.5 FOLLOW-UP OF PATIENTS AFTER ADVERSE EVENTS

5.5.1 Investigator Follow-Up

The investigator should follow each adverse event until the event has resolved to baseline grade or better, *or* the event is assessed as stable by the investigator, *or* the patient is lost to follow-up, or the patient withdraws consent. Every effort should be made to follow all serious adverse events considered to be related to study drug or trial-related procedures until a final outcome can be reported.

During the adverse event reporting period (defined in Section 5.3.1), resolution of adverse events (with dates) should be documented on the Adverse Event eCRF and in the patient's medical record to facilitate source data verification.

All pregnancies reported during the study should be followed until pregnancy outcome, *with follow-up information on the infant collected according to procedures outlined in Section 5.4.3.*

5.5.2 Sponsor Follow-Up

For serious adverse events, adverse events of special interest, and pregnancies, the Sponsor or a designee may follow up by telephone, fax, electronic mail, and/or a monitoring visit to obtain additional case details and outcome information (e.g., from hospital discharge summaries, consultant reports, autopsy reports) in order to perform an independent medical assessment of the reported case.

5.6 ADVERSE EVENTS THAT OCCUR AFTER THE ADVERSE EVENT REPORTING PERIOD

The Sponsor should be notified if the investigator becomes aware of any serious adverse event or non-serious adverse event of special interest that occurs after the end

of the adverse event reporting period (defined as 90 days after the last dose of neoadjuvant or adjuvant atezolizumab, whichever occurs last; see [Table 5](#)), if the event is believed to be related to prior study drug treatment. These events should be reported through use of the Adverse Event eCRF. However, if the EDC system is not available, the investigator should report these events directly to the Sponsor or its designee, either by faxing or by scanning and emailing the *paper Clinical Trial Adverse Event/Special Situations Form* using the fax number or email address provided to investigators.

5.7 EXPEDITED REPORTING TO HEALTH AUTHORITIES, INVESTIGATORS, INSTITUTIONAL REVIEW BOARDS, AND ETHICS COMMITTEES

The Sponsor will promptly evaluate all serious adverse events and adverse events of special interest against cumulative product experience to identify and expeditiously communicate possible new safety findings to investigators, IRBs, ECs, and applicable health authorities based on applicable legislation.

To determine reporting requirements for single adverse event cases, the Sponsor will assess the expectedness of these events using the following reference document:

- Atezolizumab Investigator's Brochure

The Sponsor will compare the severity of each event and the cumulative event frequency reported for the study with the severity and frequency reported in the applicable reference document.

Reporting requirements will also be based on the investigator's assessment of causality and seriousness, with allowance for upgrading by the Sponsor as needed.

6. STATISTICAL CONSIDERATIONS AND ANALYSIS PLAN

The objective of this study is to determine if atezolizumab 1200 mg q21d demonstrates efficacy in the neoadjuvant setting by producing a major pathologic response rate of at least 15%; major pathologic response is defined as $\leq 10\%$ of viable tumor cells (Hellmann et al. 2014). Tumors without radiographic response, but which demonstrate a major pathologic response (Hellmann et al. 2014) will be counted as a response.

Safety of atezolizumab in this treatment setting will also be assessed.

Details of the analyses are provided in the Statistical Analysis Plan (SAP).

6.1 DETERMINATION OF SAMPLE SIZE

The primary objective of this study is to determine the major pathologic response rate. If there is evidence that the major pathologic response rate is at least 15% then there will be further consideration for the testing of atezolizumab in neoadjuvant lung cancer. This is a single-arm study, and all patients will be treated with atezolizumab. The primary endpoint is assessed by a statistical test of a single proportion of responders against the

simple alternative of 5% response. This design provides 95% statistical power to detect a difference of 10% (15% vs. 5%) at a significance level of 0.05 (1-sided test, variance of the test statistic calculated under the alternative hypothesis). To achieve this, approximately 180 patients will be enrolled in this study. At the final analysis (after 180 patients are enrolled), if there are at least 17 patients who respond then the statistical test rejects the null hypothesis of a 5% response rate in favor of a higher response rate.

This study includes one interim analysis to assess futility after 90 patients are assessed. The non-binding futility interim boundary satisfies conditional power of 0.30. Thus, the probability that the statistical test at the final analysis will be significant at the specified power and test level is at least 0.30, conditional on the data available at the time of the interim analysis. At the interim analysis, if there are seven or fewer responders out of 90 patients then the conditional power of the study drops below 0.30, and enrollment into the study may be terminated. [Table 8](#) summarizes the simulated probabilities of stopping at the interim and the final analysis for different values of major pathologic response. Note that simulated probabilities not identical to calculated probabilities due to the discrete nature of response.

Table 8 Simulated Probabilities of Stopping at the Interim and Final analysis for Different Values of Major Pathologic Response

True Major Pathologic Response Rate	Probability of Stopping at Interim	Probability of Continuing to Final	Simulated Power
0.05	0.84	0.16	3%
0.10	0.19	0.81	72%
0.15	0.01	0.99	99%

Note: Simulated probabilities are not identical to calculated probabilities due to the discrete nature of response.

Differential response by PD-L1 status (positive vs. negative) will also be assessed. While the composition of PD-L1 status in this patient population is not known, the study will aim to include at least 60 PD-L1-positive patients. With 60 patients, the one-sided 95% CI excludes 20% if the major pathologic response rate is 30% (18 responders out of 60 patients). Final enrollment numbers may be expanded accordingly.

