### **6.3 Efficacy Analysis**

#### **6.3.1 Primary Efficacy Analysis**

The number of subjects with major pathologic response (n) and the major pathologic response rate ( $n/N \times 100$ ) will be summarized for the primary efficacy population (N). A one sample exact binomial test will be performed to test the null hypothesis that the major pathologic response rate is 5%, versus the alternative hypothesis is the major pathologic response rate is  $> 5\%$ . If the null hypothesis is rejected then this is evidence that the response rate exceeds 5% when atezolizumab is given before resection. The one-sided 95% confidence interval (CI) for major pathologic response rate will be reported.

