##### 6.5.1.2 *Planned Interim Efficacy Analysis*

The study includes one interim analysis to assess futility after 90 patients are assessed for MPR. The non-binding futility interim boundary satisfies conditional power at a cut-off of 0.30.

The analysis for the primary endpoint will be conducted and assessed against the futility boundary. If there are 7 or fewer responders out of 90 patients, then the conditional power of the study drops below 0.30, and enrollment may be terminated.

Outputs from this SAP which will facilitate the planned interim efficacy analysis are flagged in Section 9 of this SAP.

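### The plan mixes two primary tests: the sample-size text rejects at 17 of 180 and stops at 7 of 90, the SAP's exact test rejects from 15, and Table 8 does not describe the printed rule

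*Protocol*

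**What the plan says.** The sample-size text (Protocol Synopsis, Protocol 6.1, SAP 6.1.4) sets out a one-sided 0.05 test of 5% against 15% with 95% power and about 180 patients, with "variance of the test statistic calculated under the alternative hypothesis". For the final analysis it says that "if there are at least 17 patients who respond then the statistical test rejects the null hypothesis of a 5% response rate". For the single futility look, non-binding and set at conditional power 0.30, it says that "if there are seven or fewer responders out of 90 patients then the conditional power of the study drops below 0.30". SAP 6.5.1.2 repeats that count: "If there are 7 or fewer responders out of 90 patients, then the conditional power of the study drops below 0.30". No passage names the response rate assumed for the remaining patients in the conditional power.

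Protocol 6 refers the reader to the SAP for analysis detail. SAP 6.3.1 says: "A one sample exact binomial test will be performed to test the null hypothesis that the major pathologic response rate is 5" per cent, with a one-sided 95% confidence interval. SAP 6.6 declares no departure from the protocol.

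Protocol 6.1 also carries Table 8, titled "Simulated Probabilities of Stopping at the Interim and Final analysis for Different Values of Major Pathologic Response". At true rates of 5/10/15% it shows stopping 0.84/0.19/0.01, continuing 0.16/0.81/0.99 and power 3%/72%/99%. Its note reads: "Simulated probabilities are not identical to calculated probabilities due to the discrete nature of response".

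**The concern.** A single-arm trial with one binary endpoint needs one rejection rule, one futility rule and operating characteristics computed from those rules. Here the count in the sample-size text and the test in the SAP's analysis section appear to disagree, and the table printed just below the rules appears to belong to other rules.

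Two decisions are exposed. At the end, a count between the two cut-offs would be a success under one section and a failure under another, within the SAP itself. At the interim, exactly 7 of 90 permits stopping under the text, while Table 8's stopping probabilities treat that result as continuing. A reader relying on Table 8 would also overestimate the chance of success at a true rate of 10%.

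**Working it through.** **Inputs.** Null 5%, alternative 15%, one-sided 0.05, N=180, interim at 90, conditional power 0.30, rejection at 17, futility at 7 (Protocol 6.1, SAP 6.1.4); exact test (SAP 6.3.1); Table 8 (Protocol 6.1). One assumption is added: conditional power uses the observed trend.

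**1. Reproducing the text.** The z-test has variance 0.15 x 0.85 = 0.1275.
- Final cut-off: 180 x (0.05 + 1.645 x sqrt(0.1275/180)) = 16.88, so 17.
- Interim at half the information: conditional power 0.30 under the observed trend requires z = (1.645 - 0.524 x sqrt(0.5))/sqrt(2) = 0.901. As a count this is 90 x (0.05 + 0.901 x sqrt(0.1275/90)) = 7.55, so stop at 7 or fewer.
- Power at 15%: the final z has mean 0.10/sqrt(0.1275/180) = 3.757 and the interim z has mean 3.757 x sqrt(0.5) = 2.657, with correlation 0.707. P(interim z > 0.901 and final z > 1.645) = 95.2%. N=179 also reaches 95%.

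So 17, 7, 180 and 95% all follow from one z-test design.

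**2. The exact test of SAP 6.3.1 at N=180.** P(X>=r) is as follows:

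| r | at 5% | at 10% | at 15% |
|---|---|---|---|
| 14 | 0.069 | 0.871 | 0.999 |
| 15 | 0.037 | 0.806 | 0.997 |
| 16 | 0.019 | 0.726 | 0.995 |
| 17 | 0.009 | 0.634 | 0.989 |

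The exact test rejects from 15. A cut-off of 17 has exact size 0.9%.

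**3. Table 8 against the printed rules.** The stopping column depends only on the binomial count out of 90; rejection adds the second 90.

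| Rule | Stop at 5/10/15% | Reject at 5/10/15% |
|---|---|---|
| Table 8 | 0.84/0.19/0.01 | 3%/72%/99% |
| Printed: stop <=7, reject >=17 | 0.92/0.31/0.03 | 0.7%/54%/96% |
| Stop <=7, reject >=15 | 0.92/0.31/0.03 | 2.2%/64%/97% |
| Stop <=6, reject >=15 | 0.84/0.19/0.01 | 2.9%/72%/99% |

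With stopping at 7 or fewer, only 68.9% of trials continue at a true 10% and 96.9% at 15%. No final cut-off can then give 72% and 99%. Among rules for N=180, only stop at 6 with reject at 15 fits every cell.

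The note on discreteness does not explain the gap, because these are exact discrete probabilities. Nor does simulation error: with an assumed 1,000 runs the standard error of 0.312 is 0.0147, and (0.312 - 0.19)/0.0147 is about 8.

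**4. Conditional power, exact, observed trend.** With cut-off 17 it is 0.16 at 7 of 90 and 0.41 at 8, which gives the printed count. With cut-off 15 it is 0.15 at 6 and 0.40 at 7, which gives six or fewer.

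**5. Size of the disputed zone.** The chance of ending on 15 or 16 of 180 at 5/10/15% is 2.8%/17.1%/0.8% without an interim, and 1.5%/9.5%/0.5% with stopping at 7 or fewer.

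**6. Other N (assumed values).** SAP 5 can take the analysed N below 180. At 160/150/140 the exact cut-off is 14/13/12 and the z cut-off 16/15/14. The sample-size text also allows expansion. At 210 the exact cut-off is itself 17; at 240 a fixed 17 has size 9.6%.

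**The case against.** The strongest reply is that little turns on this. SAP 6.3.1 states the operative analysis as a test, so the analyst has an instruction, and 17 appears only in sample-size sections. The boundary is non-binding. The zone of 15 or 16 of 180 is a rate of 8.3% to 8.9%, and at 16 the one-sided exact 95% upper limit is 13.2%. Since Protocol 6.1 ties further development to evidence of at least 15%, neither label for 15 or 16 responders would meet that condition. All of this stands and limits the severity. It does not remove the conflict: SAP 6.1.4 words 17 as the point at which the test rejects, the futility count is repeated as an operating rule in SAP 6.5.1.2, and Table 8 itself counts futility stops.

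A reader might also infer that 180 and 95% are unexplained, because the z formula needs only (1.645 + 1.645)^2 x 0.1275/0.01 = 138 patients. The documents do not support this. The 138 ignores the futility stop; with it, 138 patients give 89.9% and 180 give 95.2%. Similarly, the futility count is not beyond checking: the rate is unstated, but the observed trend reproduces 7.

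Finally, a reader might take Table 8 as proof that the exact test was the intended design. It is not. The same conditional-power criterion with the variance at 5% has an interim cut-off of 6.36, so it also stops at 6 or fewer. Its final cut-off is 14 (13.81), which does not fit the power column (76% at a true 10%). The table shows that the printed rules were not used, not which test was meant.

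**Conclusion.** The inconsistency is real and should be fixed. The sample-size text is coherent with itself as a z-test design (17, 7, 180, 95%), assuming observed-trend conditional power. SAP 6.3.1 uses a different test, with cut-off 15 at N=180. Table 8 matches neither the printed futility count nor the printed rejection count, and overstates success at a true 10% by about 18 points (72% against 54%) if the printed rules are followed. That stop-at-6, reject-at-15 lies behind the table is inferred.

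It would be wrong to read this as inflated type I error. At N=180 or below both rules stay under 5%, and non-binding futility does not raise it. That reassurance lapses for a fixed 17 if enrollment is expanded far enough. The final-count conflict has little effect at true rates of 5% and 15% and matters mainly in between.

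**What to change.** Choose one test and use it in the Protocol Synopsis, Protocol 6.1, SAP 6.1.4, SAP 6.3.1 and SAP 6.5.1.2. State the final criterion as a function of the N analysed, name the rate used for conditional power, and make Table 8 and the power statement match. Which test is the sponsor's choice.

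- **Option A, exact test.** Reject if the one-sided exact p is 0.05 or less (15 or more if N=180). Stop at six or fewer of 90 (observed-trend conditional power 0.15 at 6, 0.40 at 7). Keep Table 8 and delete the alternative-variance phrase. Replace the 95% with exact figures at N=180: size 2.9% and power 98.6% with the stop, 3.7% and 99.7% ignoring it. Note that 180 came from the normal-approximation design with futility.
- **Option B, z-test.** Keep 17, 7, 180 and 95%, labelling the 95% as the normal-approximation result with futility (exact power 96.4% with the stop) and 17 as the value for N=180. In SAP 6.3.1 substitute that z-test and its matching one-sided limit, the observed rate minus 1.645 x sqrt(0.1275/N): 4.51% at 16/180, 5.07% at 17/180. Replace Table 8 with stopping 0.92/0.31/0.03, continuing 0.08/0.69/0.97 and rejection 0.7%/54%/96%.

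The cost is text and number edits, with no patients and no new data. Option A lowers the written bar from 17 to 15; Option B gives up the exact test and accepts 54% success at a true 10%. The trial is open-label, and Protocol 6.7.2 and SAP 6.5.2 allow sponsor staff extra efficacy looks, so date the change before the primary analysis and any further look. If responder counts are already known, record them and report the result under both rules.
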